4. SUBJECT POPULATION

Screening of subjects will be performed within 35 days before randomization. The inclusion and exclusion criteria for enrolling subjects in this study are described in the following 2 subsections. If there is a question about the inclusion or exclusion criteria below, then the investigator must consult with the appropriate sponsor representative and resolve any issues before enrolling a subject in the study. Waivers are not allowed. For the purpose of this study, a subject that is randomized is considered enrolled.

4.1. Inclusion Criteria

Each potential subject must satisfy all of the following criteria to be enrolled in the study:

1. At least 18 years of age or at least the legal age of consent in the jurisdiction in which the study is taking place, whichever is the older age.
2. Criterion amended per Amendment 1:
 - 2.1 Diagnosis of SMM (per IMWG criteria) for ≤ 5 years with measurable disease at the time of randomization, defined as serum M protein ≥ 10 g/L or urine M protein ≥ 200 mg/24 hours or involved serum FLC ≥ 100 mg/L and abnormal serum FLC ratio.
3. Criterion amended per Amendment 1:
 - 3.1 Clonal BMPCs $\geq 10\%$; and
 - At least 1 of the following risk factors;
 - a. Serum M protein ≥ 30 g/L,
 - b. IgA SMM,
 - c. Immunoparesis with reduction of 2 uninvolved immunoglobulin isotypes (only IgA, IgM, and IgG should be considered in determination for immunoparesis; IgD and IgE are not considered in this assessment),
 - d. Serum involved: uninvolved FLC ratio ≥ 8 and < 100 , or
 - e. Clonal BMPCs $> 50\%$ to $< 60\%$ with measurable disease.
4. ECOG performance status score of 0 or 1 ([Attachment 1](#)).
5. Pretreatment clinical laboratory values meet the following criteria during the Screening Phase:
 - a. Absolute neutrophil count $\geq 1.0 \times 10^9/L$ (ie, $\geq 1000/\mu L$)

- b. Platelet count $\geq 50 \times 10^9/L$ (not permissible to transfuse a subject within 2 weeks prior to the Screening platelet count to reach this level)
- c. Aspartate aminotransferase (AST) $\leq 2.5 \times$ upper limit of normal (ULN)
- d. Alanine aminotransferase (ALT) $\leq 2.5 \times$ ULN
- e. Total bilirubin $\leq 2.0 \times$ ULN, except in subjects with congenital bilirubinemia, such as Gilbert syndrome (in which case direct bilirubin $\leq 2.0 \times$ ULN is required)

6. Must sign an informed consent form (ICF) or their legally designated representative must sign indicating that he or she understands the purpose of, and procedures required for, the study and is willing to participate in the study.

7. Criterion amended per Amendment 1:

7.1 Contraceptive use by men or women should be consistent with local regulations regarding the use of contraceptive methods for subjects participating in clinical studies.

Women of childbearing potential must commit to either abstain continuously from heterosexual sexual intercourse or to use 1 method highly effective form of contraception (tubal ligation, intrauterine device, hormonal [birth control pills, injections, hormonal patches, vaginal rings or implants], or partner's vasectomy). Contraception must begin 4 weeks prior to dosing. Highly effective contraception is indicated even where there has been a history of infertility, unless due to hysterectomy. See [Attachment 11](#) for definitions of Women of Childbearing Potential

8. A woman of childbearing potential must have a negative serum or urine pregnancy test at screening within 14 days prior to randomization. For requirements during the Treatment Phase, see Section [4.3](#)

9. During the study and for 3 months after receiving the last dose of daratumumab, a woman must agree not to donate eggs (ova, oocytes) for the purposes of assisted reproduction.

10. Willing and able to adhere to the prohibitions and restrictions specified in this protocol.

4.2. Exclusion Criteria

Any potential subject who meets any of the following criteria will be excluded from participating in the study:

1. Criterion amended per Amendment 2:
- 1.1 Multiple myeloma, requiring treatment, defined by any of the following:

- a. Bone lesions (one or more osteolytic lesions on low-dose whole body computed tomography [LDCT], positron-emission tomography with computed tomography [PET-CT] or CT). Subjects who have benign/post-traumatic bone lesions visible on screening images as well as previous imaging, may be considered for inclusion. Details (diagnosis, location, duration) on benign/post-traumatic pre-existing bone lesions that can be seen on the screening images (eg, old fractures) and were also present on previous imaging are to be reported in the CRF (see Section 9.1.2 and Section 9.2.7).
- b. Hypercalcemia (serum calcium >0.25 mmol/L [>1 mg/dL] higher than ULN or >2.75 mmol/L [>11 mg/dL]). Subjects who have clinically stable hypercalcemia attributable to a disease other than multiple myeloma (eg, hyperparathyroidism) may be considered for inclusion after a case by case review by the medical monitor (see Section 9.2.3).
- c. Renal insufficiency, preferably determined by creatinine clearance <40 mL/min measured or estimated using the MDRD ([Attachment 2](#)), or serum creatinine >177 μ mol/L. Subjects who have clinically stable renal insufficiency attributable to a disease other than multiple myeloma (eg, glomerulonephritis) may be considered for inclusion after a case by case review by the medical monitor (see Section 9.2.3).
- d. Anemia, defined as hemoglobin <10 g/dL or >2 g/dL below lower limit of normal or both; transfusion support or concurrent treatment with erythropoietin stimulating agents is not permitted. Subjects who have clinically stable anemia attributable to a disease other than multiple myeloma (eg, thalassemia, vitamin B12 deficiency, iron deficiency) may be considered for inclusion after a case by case review by the medical monitor (see Section 9.2.3). (Refer to [Appendix 18.1](#) for specific requirements for France.)
- e. Clonal BMPC percentage $\geq 60\%$
- f. Serum FLC ratio (involved:uninvolved) ≥ 100 (The involved FLC must be ≥ 100 mg/L)
- g. More than 1 focal lesion ≥ 5 mm in diameter by MRI

2. Primary systemic AL (immunoglobulin light chain) amyloidosis.
3. Criterion amended per Amendment 2:
 - 3.1 Exposure to any of the following
 - a. Prior exposure to daratumumab or prior exposure to other anti-CD38 therapies

- b. Prior exposure to approved or investigational treatments for SMM or MM (including but not limited to conventional chemotherapies, IMiDs, or PIs). Stable standard dosing of bisphosphonate and denosumab as indicated for osteoporosis is acceptable.
- c. Exposure to investigational drug (including investigational vaccines) or invasive investigational medical device for any indication within 4 weeks or 5 half-lives, whichever is longer, before Cycle 1, Day 1
- d. Ongoing treatment with corticosteroids with a dose >10 mg prednisone or equivalent per day at the time of randomization; or >280 mg cumulative prednisone dose or equivalent for any 4-week period in the year prior to randomization
- e. Ongoing treatment with other monoclonal antibodies (eg, infliximab, rituximab), immunomodulators (eg, abatacept, methotrexate, azathioprine, cyclosporine) or other treatments that are likely to interfere with the study procedures or results

4. Received treatment (chemotherapy, surgery, etc) for a malignancy (other than SMM) within 3 years before the date of randomization (exceptions are squamous and basal cell carcinomas of the skin, carcinoma in situ of the cervix or breast, or other non-invasive lesion), which is considered cured with minimal risk of recurrence within 3 years.

5. Either of the following:

- a. Known or suspected chronic obstructive pulmonary disease (COPD) with a forced expiratory volume in 1 second (FEV1) <50% of predicted normal
- b. Moderate or severe persistent asthma within the past 2 years (see [Attachment 3](#)), or currently has uncontrolled asthma of any classification. (Note that subjects who currently have controlled intermittent asthma or controlled mild persistent asthma are allowed in the study).

The LDCT/PET-CT/CT performed for screening should be taken into consideration to determine if additional pulmonary workup is required.

6. Criterion amended per Amendment 1:

6.1 Criterion modified per Amendment 3:

6.2 Any of the following:

- a. Known to be seropositive for human immunodeficiency virus (HIV)
- b. Seropositive for hepatitis B (defined by a positive test for hepatitis B surface antigen [HBsAg]). Local testing and results of hepatitis B serology (Includes

HBsAg, anti-HBs, and anti-HBc) is required for all patients prior to randomization when this amendment 3 is implemented. Subjects with resolved infection (ie, subjects who are HBsAg negative but positive for antibodies to hepatitis B core antigen [Anti-HBc] and/or antibodies to hepatitis B surface antigen [Anti-HBs]) must be screened using real-time polymerase chain reaction (PCR) measurement of hepatitis B virus (HBV) DNA levels. Those who are PCR positive will be excluded. EXCEPTION: Subjects with serologic findings suggestive of HBV vaccination (Anti-HBs positivity as the only serologic marker) AND a known history of prior HBV vaccination, do not need to be tested for HBV DNA by PCR

- c. Known to be seropositive for hepatitis C (except in the setting of a sustained virologic response [SVR], defined as aviremia at least 12 weeks after completion of antiviral therapy)
7. Medical or psychiatric condition or disease (eg, active systemic disease [including presence of auto-antibodies], uncontrolled diabetes) that is likely to interfere with the study procedures or results, or that in the opinion of the investigator, would constitute a hazard for participating in this study.
8. Clinically significant cardiac disease, including:
 - a. myocardial infarction within 6 months with left ventricular dysfunction or uncontrolled ischemic cardiac disease before Cycle 1 Day 1, or unstable or uncontrolled disease/condition related to or affecting cardiac function (eg, unstable angina, congestive heart failure, New York Heart Association Class III-IV)
 - b. Uncontrolled cardiac arrhythmia (Grade 2 or higher by National Cancer Institute-Common Terminology Criteria for Adverse Events [NCI-CTCAE] Version 4.03) or clinically significant ECG abnormalities
 - c. Screening 12-lead ECG showing a baseline QT interval as corrected QT interval corrected for heart rate >470 msec.

The LDCT/PET-CT/CT performed for screening should be taken into consideration to determine if additional cardiac workup is required.

9. Criterion amended per Amendment 1:
 - 9.1 Known allergies, hypersensitivity, or intolerance to corticosteroids, monoclonal antibodies, hyaluronidase, or other human proteins, or their excipients (refer to Daratumumab Investigator Brochure¹¹), or known sensitivity to mammalian-derived products (including dairy allergy).

10. Vaccination with live attenuated vaccines within 4 weeks of first study agent administration
11. Pregnant, breast-feeding, or planning to become pregnant while receiving study treatment or within 3 months after the last dose of daratumumab
12. Plans to father a child while receiving study treatment or within 3 months after the last dose of daratumumab
13. Major surgery (requiring general anesthesia or presence of other factors that determines surgery to be considered major) within 2 weeks before randomization or who have not fully recovered from surgery, or has surgery planned during the time the subject is expected to participate in the study or within 2 weeks after the last dose of daratumumab. Note: subjects with planned surgical procedures to be conducted under local anesthesia may participate. If there is a question whether a procedure is considered a major surgery, then the investigator must consult with the appropriate sponsor representative and resolve any issues before enrolling a subject in the study.
14. Known or suspected of not being able to comply with the study protocol (eg, because of alcoholism, drug dependency, or psychological disorder). Subject has any condition for which, in the opinion of the investigator, participation would not be in the best interest of the subject (eg, compromise the well-being) or that could prevent, limit, or confound the protocol-specified assessments. Subject is taking any prohibited medications.

NOTE: Investigators should ensure that all study enrollment criteria have been met at screening. If a subject's clinical status changes (including any available laboratory results or receipt of additional medical records) after screening but before the start of the Active Monitoring Phase (Arm A) or the first dose of daratumumab (Arm B) is given, such that he or she no longer meets all eligibility criteria, then the subject should be excluded from participation in the study. Section 17.4, Source Documentation, describes the required documentation to support meeting the enrollment criteria. Subjects who fail to meet the inclusion and exclusion criteria (ie, screen failures) may be rescreened if their condition changes. Rescreening must be discussed with and approved by the sponsor on a case-by-case basis. Subjects who are determined to be eligible for the study after rescreening must sign a new ICF and then will be assigned a new Subject number.

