	Notes	Active Monitoring (Arm A; 12-week disease evaluations) / Treatment Phase (Arm B; 4-week treatment cycles after Cycle 6) ^a (up to 39 cycles or 36 months, whichever occurs first)						End of Active Monitoring/ End of Treatment	Pre-PD Follow-up	PD	Post-PD Follow-up	
		Screening (within 35 days before randomization)	C1-2		C3-6		C7-39					
		D1 ^b	D8	D15	D22	D1	D15	D1	30 (±3) days after the last Daratumumab dose ^c	every 12 weeks (±7 days)	at least every 6 months (until end of study)	
		Daratumumab (Arm B): Continuous from the time of signing of ICF until 30 days after last daratumumab dose, or until start of next therapy, whichever is earlier.										
Survival, Second primary malignancies		Throughout study until the end of study, and at a frequency of at least every 12 weeks until PD.										X
Best response to first-line MM treatment, PFS2	Investigator review; no central laboratory testing											X
Biomarkers Assessments. Per Amendment 6 all biomarker assessments by central lab are discontinued. FISH testing at PD to be performed locally.												
Whole blood (biomarkers)	Cytometry by time of flight	X	Week 24, Week 48, Week 96, and at suspected CR (±1 month with disease evaluations)					X		X		
	PBMCs	X										
	Plasma	X	Every 12 months from C1D1 (±1 month with disease evaluations)							X		
Stool (biomarkers)	Microbiome	X	Week 24 and at suspected CR (±1 month with disease evaluations)							X		
Bone Marrow aspirate ^m	Cytogenetics by FISH ^k	X								X		

Notes	Active Monitoring (Arm A; 12-week disease evaluations) / Treatment Phase (Arm B; 4-week treatment cycles after Cycle 6) ^a (up to 39 cycles or 36 months, whichever occurs first)						End of Active Monitoring/ End of Treatment	Pre-PD Follow-up	PD	Post-PD Follow-up
	Screening (within 35 days before randomization)	C1-2		C3-6		C7-39				
		D1 ^b	D8	D15	D22	D1	D15	D1		

- a. Treatment Phase (Arm B): daratumumab SC administered weekly in Cycles 1 and 2, every 2 weeks for Cycles 3 to 6, and every 4 weeks thereafter until 39 cycles or 36 months (whichever occurs first) or confirmed PD.
- b. C1D1 should occur within 5 days after randomization (Arm B).

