9.1.3. Active Monitoring Phase or Treatment Phase

Details of the procedures performed during the Active Monitoring Phase (Arm A) and the Treatment Phase (Arm B) are outlined in the Time and Events Schedule (Table 1). Subjects in the daratumumab arm (Arm B) should start study treatment within 5 days after randomization. Active monitoring of subjects in Arm A will start immediately after randomization. All subjects will be closely monitored for adverse events, laboratory abnormalities, and clinical response. Clinical evaluations and laboratory studies may be repeated more frequently, if clinically indicated. If disease progression is confirmed in a subject during the Active Monitoring Phase, then the subject will discontinue active monitoring, complete the End-of-Active Monitoring Visit, and enter the Follow-up Phase. For subjects in the Active Monitoring (Arm A), the End-of- Active-Monitoring visit is to be performed within 30 days (± 3 days) of confirmation of disease progression by investigator. If disease progression is confirmed in a subject in the daratumumab arm, then the subject will discontinue study treatment, complete the End-of-Treatment Visit (30 days ± 3 days after the last dose of daratumumab, or before starting subsequent therapy, if earlier), and enter the Follow-up Phase. Biochemical progression without meeting diagnostic criteria for MM (Table 9) does not constitute a reason to discontinue study treatment.

End-of-Active Monitoring Visit (Arm A)/End-of-Treatment Visit (Arm B)

Unless a subject withdraws consent for study participation or is lost to follow-up, an End-of-Active Monitoring Visit (Arm A)/End-of-Treatment (Arm B) Visit is to occur. For subjects in Arm A, the End-of Active Monitoring Visit is to occur after 36 months (± 3 days) (from the date of randomization) of active monitoring if disease progression was not yet confirmed earlier, or if the subject did not meet other criteria for discontinuation prior to 36 months (refer to Section 10.2).

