9.2.4. Myeloma Protein Measurements in Serum and Urine

Per protocol Amendment 6, M-protein measurements will no longer be analyzed by the central laboratory and will only be analyzed locally.

The following tests will be performed.

- Serum quantitative immunoglobulins (QIgs): All subjects will be evaluated for IgG, IgA, IgM, IgE, and IgD at Screening. During the study, subjects with IgD or IgE disease will be evaluated for IgG, IgA, IgM, IgE, and IgD and subjects with IgG, IgA, or IgM disease will be evaluated for IgG, IgA, and IgM.
- Serum M-protein quantification by electrophoresis (SPEP)

- 24-hour urine M-protein quantitation by electrophoresis (UPEP)
- Serum immunofixation electrophoresis (SIFE)/urine immunofixation electrophoresis
- Serum FLC assay

Blood and 24-hour urine samples for disease assessments will be collected during screening and as specified in the Time and Events Schedule ([Table 1](#)) until the development of PD. If blood and 24-hour urine disease assessment samples collected at screening were taken within 14 days before Cycle 1 Day 1, then it is not mandatory to collect these samples again at the Cycle 1 Day 1 visit. Repeat laboratory studies in cases where screening values were obtained >14 days from Cycle 1 Day 1 only need to be obtained for Arm B subjects.

In subjects with a baseline UPEP result below the level of measurable disease (<200 mg/24 hours), UPEP analysis will be repeated only at the time of suspected CR. Serum/urine immunofixation assays will be performed at screening, and at other times if considered helpful in the interpretation of SPEP and UPEP results. In subjects without measurable disease in the urine at diagnosis who show rising involved serum FLC (or raise other clinical concerns), UPEP may be performed at the investigator's discretion to assess for excretion of light chains. Baseline value is defined as the last value prior to initiating treatment (Arm B) or prior to randomization for active-monitoring subjects (Arm A).

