**Table 4: PFS Event and Censoring Method**

Situation	Date of Progression or Censoring	Outcome
No postbaseline disease assessment	Randomization	Censored
Disease progression prior to start of anti-cancer therapy for multiple myeloma	Earliest date that indicates disease progression	PFS event
Death prior to start of anti-cancer therapy for multiple myeloma	Date of death	PFS event
Other, such as: 
 
○ Withdrawal of consent to study participation,
 
○ Lost to follow-up
 
○ Start of subsequent anti-cancer therapy prior to disease progression or death
 
	Date of last disease assessment on or prior to withdrawal of consent to study participation, lost to follow-up, or start of subsequent anti-cancer therapy	Censored

Note, Subjects who were already diagnosed multiple myeloma per baseline central imaging review will be censored at randomization.

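### After randomization, the Section 4.2 NOTE can exclude a subject for lost eligibility only in Arm B, and the plan does not say that PFS follow-up then continues

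*Protocol*

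**What the plan says.** The NOTE closing Protocol Section 4.2 concerns a change in clinical status "after screening but before the start of the Active Monitoring Phase (Arm A) or the first dose of daratumumab (Arm B) is given". If the change is "such that he or she no longer meets all eligibility criteria, then the subject should be excluded from participation in the study".

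The two end points of that window fall at different times. Under Protocol Section 9.1.3, "Active monitoring of subjects in Arm A will start immediately after randomization", whereas Arm B subjects "should start study treatment within 5 days after randomization". Table 1 footnote b repeats the 5-day limit.

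Testing in the window also differs. Under Section 9.2.4 and Table 1 footnote g, repeat laboratory studies for screening values more than 14 days before Cycle 1 "Day 1 only need to be obtained for Arm B subjects".

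These subjects already belong to the trial. Section 4 says: "For the purpose of this study, a subject that is randomized is considered enrolled". SAP Section 2.3.1.1 places all randomized subjects in the ITT set, as randomized. In SAP Table 4 a subject with "No postbaseline disease assessment" is censored at randomization.

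**The concern.** An exclusion made after randomization, available in one arm only and decided with the allocation known, departs from a like-for-like comparison. Here it is also tied to the primary endpoint. The exclusion limits for calcium, renal function, hemoglobin and FLC ratio in Section 4.2 (criterion 1.1) are close to the limits for progression to myeloma in Table 9. A subject excluded for crossing one of them may be an early progressor.

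If exclusion stops disease evaluation, that subject contributes no PFS time and no event. A comparable Arm A subject is not re-tested at that point, stays under 12-weekly evaluation, and can become an event once progression is confirmed. Any such loss lowers the estimated hazard ratio (daratumumab versus active monitoring).

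**Working it through.** **1. Window after randomization.** Arm A: 0 days. Arm B: up to 5 days. Before randomization the NOTE is an ordinary screen-failure rule acting on both arms alike.

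**2. Age of screening laboratory values.** Screening runs up to 35 days before randomization (Section 4), so values can be 35 + 5 = 40 days old at Cycle 1 Day 1. The Arm B repeat applies beyond 14 days.

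**3. The plan's own figure.** Inputs from Protocol Section 11.2: hazard ratio 0.625, one-sided alpha 0.025, power 85%, 165 events. Schoenfeld: 4 × (1.960 + 1.036)² / (ln 0.625)² = 163 events. At 165 events the power is 85.5%. The plan's figure reproduces.

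**4. Expected Arm B progressions in the window.** Control median 30 months, constant hazard λ = ln 2 / 30 = 0.0231 per month; month = 30.44 days; 180 subjects. Number = 180 × [1 − exp(−λ × days / 30.44)].

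| Interval | Risk per subject | Of 180 |
|---|---|---|
| 5 days (dosing window only) | 0.38% | 0.7 |
| 15 days (just past the 14-day rule) | 1.1% | 2.0 |
| 40 days (oldest possible values) | 3.0% | 5.4 |

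**5. Effect on the hazard ratio.** Each scenario used 5,000 simulated event-driven trials (360 subjects, uniform 24-month accrual, analysis at 165 events, unstratified log-rank and Cox). Every Arm B subject progressing in the interval was either kept or censored at time 0. The hazard before dosing was the control hazard in both arms. The 40-day case counts the interval as time after randomization, a simplification.

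| Interval | True HR | HR, kept | HR, censored | One-sided rejection under the null, kept → censored |
|---|---|---|---|---|
| 5 days | 1.0 | 1.000 | 0.992 | 0.024 → 0.027 |
| 40 days | 1.0 | 1.003 | 0.940 | 0.022 → 0.057 |
| 5 days | 0.625 | 0.630 | 0.623 | – |
| 40 days | 0.625 | 0.643 | 0.592 | – |

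The simulation standard error of the rejection rates is about 0.002 near the nominal level, so the 5-day change is of the order of simulation error. Hand check under the null, with 165 / 2 = 82.5 Arm B events: (82.5 − 0.7) / 82.5 = 0.99 and (82.5 − 5.4) / 82.5 = 0.93, in line with the simulated values.

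**6. Rules on follow-up.** Section 10.2 says that stopping treatment or monitoring does not by itself withdraw a subject from the study. Section 9.1.4 requires disease evaluations to continue in those who discontinue before progression. Section 10.3 does not name loss of eligibility as a withdrawal reason, but lets the investigator stop participation for any reason. None of them addresses a randomized subject who never starts treatment, and the NOTE refers to none of them.

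**7. Baseline.** SAP Section 2.6 ties Arm B baseline to the first dose. For a never-dosed Arm B subject it is undefined, so a Day 1 value cannot be classed as baseline or post-baseline.

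**The case against.** The strongest case against is that the chain from the NOTE to a lost event has several weak links. Most of it stands.

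- **Results before dosing.** The NOTE stops applying once the first dose is given. Table 2 footnote b requires only hematology results to be evaluated before dosing, and Day 1 hematology need not be repeated if done within 7 days. Table 2 schedules local chemistry at Cycle 2 and Cycle 3 Day 1. Section 9.7 mentions chemistry before each dosing but defers to that schedule. Repeat disease samples must be drawn before dosing; nothing requires their results by then.
- **A Day 1 crossing is usually not yet a PFS event.** Progression on laboratory values alone needs a consecutive confirming assessment, unless two of the named tests are met on the same date (Section 9.2). Other causes must be ruled out (Section 9.2.3), and the FLC criterion also needs a confirmed rise from nadir (Section 9.2.2). Eligibility can also be lost for reasons unrelated to progression.
- **ITT and event rules.** Excluded subjects stay in the ITT set, and SAP Table 4 counts documented progression or death before myeloma therapy without requiring any dose.

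A reader might infer that early Arm B progressors drop out of the analysis, that their PFS2 and OS follow-up ends, and that matching Arm A subjects become events at the next visit. The documents state none of these. Loss of follow-up is one reading of exclusion from participation, and Sections 9.1.4 and 10.2 point the other way.

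Two points survive. A subject in the ITT set who is censored at randomization carries no PFS information. And the 5-day figure counts only new progression: a repeat test can also reveal a crossing that arose since screening, which would go unnoticed in Arm A until its next evaluation.

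**Conclusion.** The point holds as an arm-dependent rule after randomization that the documents leave unreconciled, with a direction favouring daratumumab. Its severity is minor to moderate.

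Progression arising within the 5 days gives about 0.7 of 180 Arm B subjects and a null hazard ratio of about 0.99. The upper bound is about 5 of 180 and about 0.94. That bound needs all screening values to be 40 days old, every crossing to show on laboratory tests known before dosing, and every such subject to be excluded and lost to evaluation. Both cases assume a constant control hazard.

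The range of 2 to 5 subjects might be read as an expected loss. It is not one. The documents give no distribution of laboratory age and no count of excluded subjects, and values no more than 14 days old need no repeat of the disease tests, so even 2 is not a floor. If no randomized Arm B subject was excluded before dosing, the point has no numerical consequence.

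**What to change.** **Protocol.** Limit the NOTE's exclusion from the study to the period before randomization. State that a randomized subject who later fails a criterion stays in 12-weekly disease evaluation and survival follow-up and is analysed from randomization in the assigned arm, with confirmed progression under the same IMWG rules counted as an event. Reconcile the NOTE with Sections 9.1.4, 10.2 and 10.3. Whether study drug is started in such a subject is a separate decision outside this change.

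**SAP.**
- Define baseline for never-dosed Arm B subjects.
- Report, by arm and with reasons, randomized subjects who did not start their assigned phase (in Arm B, those never dosed). SAP Sections 4.2 and 4.5 already tabulate enrolled and treated subjects and major deviations, so this is a small addition.
- If any were excluded, add a PFS sensitivity analysis; none of those in SAP Section 5.2.3 covers this case. One option treats those excluded for a SLiM-CRAB criterion as events at the first scheduled 12-week evaluation, labelled as a conservative bound. Counting unconfirmed Day 1 values as events would not do: that test is required only in Arm B, so it would create the opposite bias and bypass the confirmation rule.

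**Cost.** A few protocol sentences, one table and at most one extra analysis. Keeping a few never-dosed subjects slightly dilutes the estimated effect (0.630 against 0.625 in the 5-day case). The Amendment 6 summary says the primary analysis has concluded, so the protocol change now mainly aligns the text; the reporting and sensitivity analysis are the parts that still act.
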